1.1 CTO

Chronic total occlusion (CTO) of one or more coronary vessels are relatively common findings in coronary angiography. One large-scale registry showed that up to 20% of patient with coronary artery disease had a CTO. (1) Compared to percutaneous coronary intervention (PCI) of non-occluded vessel, CTO PCI has a lower success rate, and a higher complication rate. They are time consuming and more complex, and several different strategies and various equipment is applied. This suggests more systematic procedure planning, consistent approach and a need for systematic training.(2) At most institutions, CTO PCI is performed by two operators, enabling discussions of findings and strategy during the procedure. Although only one operator at a time can be “hands on” during CTO PCI, large amounts of information is processed during the procedure, and unexpected findings and difficulties often occur. At our institution, a single operator performs CTO procedure. Procedures are often pre-planned

together with an external operator. This is helpful, but does not allow for discussion and adjustments during the intervention. We believe that CTO PCI performed in a team will be more robust and accurate than that of single operator working alone.

1.2 CTO Proctoring

Several studies have showed a relationship between physician volume and outcomes of percutaneous coronary interventions (PCI) with better outcomes reported for high volume operators when compared with low volume operators.(3) Proctoring in medicine is related to better outcomes. Specifically, in CTO PCI systematic proctoring has demonstrated improved success rates, and an increased ability to treat lesions that are more complex. (4). Most likely, proctoring together with operator volume is one of the foundations to the introduction and execution of CTO procedures. Proctoring traditionally involves an expert operator (proctor), visiting the institution, performing the procedure together with the local operator. This involves increased cost, and current travel restrictions makes traditional one-on-one proctoring challenging. To our knowledge, the feasibility of real time proctoring using modern web based communication tools has never been assessed in interventional cardiology.

1.3 Microsoft HoloLens in proctoring

This study aims to evaluate the Microsoft HoloLens as a potential platform in proctoring and effective real time communication between PCI operators located at different geographical locations. The proctor and the local operator interact using a head mounted mixed reality (MR) display, enabling the proctor to see the same image as the operator, from any distanced location.

1.4 Mixed reality in medicine

The Microsoft HoloLens is a mixed reality head mounted display, which allows users to interact with their environment using a Hologram. Mixed reality (MR) like augmented reality (AR) and virtual reality (VR) are defined like extended reality. Extended reality describes the spectrum of virtuality continuum (5). While VR are interactions fully immersed in a synthetic environment, AR allows the user to see their native environment while placing 2D or 3D images within true background. Mixed reality is a new class of experience and allows 3D visualization of imaged data and contact-free interaction with the data in the sterile environment allowing the operator to have increased control and manipulation over digital objects without obstructing the normal visual field. At the same time this technology can provide a possibility of collaboration between operators in a unique way, which can simulate the interaction as if working in a team in the same non-virtual operating space.(6)

1.5 Microsoft HoloLens in medicine

To our knowledge, this device has never been used in clinical practice connected to interventional cardiology but HoloLens and similar devices have been explored within surgical innovation (7), education in medicine (8) to treat anxiety during procedures (9) and in stroke rehabilitation (10)

In cardiological practice, mixed reality devices have been used in intraprocedural visualization connected to electrophysiology procedures (11) and in pediatric cardiology (12), (13).

We believe that communication and interaction through HoloLens or similar devices can be especially useful nowadays in a pandemic. There is an increasing interest in this subject and we expect that telemedicine and virtual interaction are going to play significant roles in the future of medicine, particularly in situations like the current health crisis. (14)

2. Study objective

2.1 Primary objective

Assess Microsoft HoloLens as an interactive communication device in remote proctoring, and enhancement of teamwork in complex CTO procedures.

2.2 Secondary objective

- a) To assess image quality, sound quality, multitasking, comfort, sterility, practicality, spatial awareness and possibility of communication with assisting nurse.
- b) Can use of HoloLens in CTO procedures increase effectiveness compared with conventional way of communication between operator and distanced proctor/co-operator
- c) Advantage of communication with HoloLens compared with traditional communication tools.
- d) To assess feasibility of using HoloLens in invasive cardiology procedures
- e) Does application of HoloLens technology cause limitations, including loss of spatial awareness, spatial disorientation, cabling, battery life and device discomfort.
- f) Does interaction between operator and proctor affect procedural endpoints like contrast volume, procedure time, fluoroscopy time, costs and procedural success

3. Methods

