3.3 Study process

Study will be conducted by two participants where one is defined as expert or proctor and the other as operator who will perform the CTO procedure. Operator carries out the procedure in our institution while expert is located 300 km away. The plan is to conduct ten CTO procedures where the operator uses Hololens during the procedure and communicates with the proctor from the beginning to the end of procedure. Expert uses conventional laptop computer connected to Hololens to communicate and guide operator.

Guiding is performed by communication (sound) and Holographic interaction through Remote Assist software or similar Hololens applications. All participants are trained how to operate Hololens.

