3.4 Statistics

3.4.1 Statistical analyses will be performed in IBM SPSS for Windows (IBM Corp., Armonk, NY, USA). Values will be presented as mean \pm standard deviation, median (interquartile range) or no (%) as appropriate.

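### Secondary objective 2.2b (and 2.2c, if a measured contrast is meant) asks for a comparison with conventional communication, but all ten planned procedures use HoloLens and no comparison data are named

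*Protocol*

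**What the plan says.** Three of the six secondary objectives in Protocol section 2.2 matter here.

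- 2.2b: "Can use of HoloLens in CTO procedures increase effectiveness compared with conventional way of communication between operator and distanced proctor/co-operator"
- 2.2c: "Advantage of communication with HoloLens compared with traditional communication tools"
- 2.2f: "Does interaction between operator and proctor affect procedural endpoints like contrast volume, procedure time, fluoroscopy time, costs and procedural success"

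The first two contain an explicit comparison. The third does not; it asks about an effect.

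The design sections are brief. Section 3.1 calls this a feasibility study and mentions no control group. Section 3.2 enrols one consecutive series. Section 3.3 plans "ten CTO procedures where the operator uses Hololens during the procedure and communicates with the proctor from the beginning to the end of procedure". Section 3.4 lists summary statistics only (mean with standard deviation, "median (interquartile range) or no (%) as appropriate") and names no contrast.

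Two background passages bear on what the comparator could be. Section 1.1 says "At our institution, a single operator performs CTO procedure", and that procedures are often planned beforehand "together with an external operator. This is helpful, but does not allow for discussion and adjustments during the intervention". Section 1.2 says "To our knowledge, the feasibility of real time proctoring using modern web based communication tools has never been assessed in interventional cardiology".

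**The concern.** A comparison needs information on both conditions. The protocol puts a comparison into its objectives, but its study process produces one condition only. The results are to be published (section 8). A statement that HoloLens raised effectiveness, or was better than conventional tools, would then answer a prespecified question with no comparison data behind it.

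This is a matter of objectives and design. No SAP was available to this review. An SAP can specify how data are analysed, but it cannot create procedures that the study process does not include.

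**Working it through.** No figure in the protocol needs reproducing. The number ten is given without a derivation, and no alpha, power, effect size or variance is stated. The check sets the sections against each other.

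**Step 1. What the planned data contain (sections 3.2 and 3.3).**

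| Condition | Planned procedures |
|---|---|
| HoloLens with proctor contact throughout | 10 |
| Any other tool for contact with a distant proctor | 0 |
| No proctor | 0 |

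**Step 2. What each objective needs.**

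- 2.2b sets HoloLens against another way of communicating with a distant colleague. It needs row 1 and row 2. Row 2 is empty, so the difference is not estimable from the planned data at any number of HoloLens procedures.
- 2.2c needs the same two rows if it means a measured contrast. If it means the users' judgement, row 1 is enough, provided that the judgement is recorded.
- 2.2f asks whether operator-proctor interaction changes the procedural endpoints. It needs row 1 and row 3. Row 3 is empty. This is a different missing reference, so repairing 2.2b and 2.2c would not repair 2.2f. Headset and proctor are also present together in every planned procedure, so the series cannot separate their effects.

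**Step 3. Whether another section supplies the missing data.**

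- *Local practice (1.1).* Pre-planning with an external operator is a form of contact with another operator. 2.2b does not say that the conventional contact must be live, so this is a possible reference. The protocol does not identify it as the comparator or as a source of data.
- *Literature (1.2).* The section says that, to the group's knowledge, the feasibility of real-time web-based proctoring is unassessed in this field. It cites evidence that systematic proctoring improved CTO success rates, but describes proctoring as traditionally done on site. No benchmark for 2.2b is designated.
- *Device removal (4.2).* The operator may take the headset off if it disturbs or is uncomfortable. The remaining part of such a procedure would be selected because of trouble, so it is not a comparison group.

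**Step 4. How far a historical reference would help (illustration).** Assume two-sided alpha 0.05, 80% power and *m* earlier procedures. None of these is in the protocol. The smallest detectable standardised mean difference is roughly (1.96 + 0.84) × √(1/10 + 1/*m*):

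| *m* | √(1/10 + 1/*m*) | Approximation (SD) | Noncentral *t* (SD) |
|---|---|---|---|
| 10 | 0.447 | 1.25 | 1.32 |
| 30 | 0.365 | 1.02 | 1.05 |
| 100 | 0.332 | 0.93 | 0.94 |

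A reference would make the question definable. Only differences of about one standard deviation would be reliably detected, which is why any such comparison should be labelled exploratory. These figures are not the defect. The defect is the 10 against 0 in step 1.

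**The case against.** The strongest reply is that this is a ten-procedure feasibility study with descriptive statistics only. No comparative test is planned, and harm arises only if the results are overclaimed. That stands as a limit on severity. It does not make 2.2b answerable.

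Three further points narrow the concern.

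- *The background might be read as ruling out every comparator.* It does not. Because 2.2b does not require live contact, the pre-planning in section 1.1 could be what is meant. What can be said is that the protocol does not name it.
- *2.2c might be read as necessarily a between-group contrast.* The text does not settle this. Beside 2.2a and 2.2e, which concern image and sound quality, comfort and limitations, it can mean advantage as judged by the users, and that needs no control group. The protocol describes no rating form, but it describes none for 2.2a either, and such a form may sit in another document. Its absence is not the finding.
- *2.2f might be said to share the defect of 2.2b.* It does not. It has no comparison phrase, lacks a different reference, and concerns procedural endpoints for which a historical series could still be named.

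**Conclusion.** The point holds for 2.2b as worded, and for 2.2c if a measured contrast is intended. With 10 HoloLens procedures, 0 comparison procedures and no named source of comparison data, the study as written cannot support a comparative conclusion. This rests on section 3.3 being followed as stated and on no comparator being defined elsewhere in the protocol; none was found.

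For 2.2f the point is lesser and separate: every procedure is proctored, so any answer about an effect needs an outside reference.

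A reader might infer that the whole study is compromised. The documents do not support that. The primary objective (2.1) and 2.2a, d and e can be addressed in a single series. The matter merits an amendment because it changes what may be concluded, but it is confined to secondary objectives.

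**What to change.** 1. Reword 2.2b and 2.2c, for example: *to describe the advantages and disadvantages of HoloLens relative to conventional tools as perceived by the operator and the proctor, rated after each procedure*. Add that no conclusion on comparative effectiveness will be drawn.
2. Alternatively, if the conventional way in 2.2b means the pre-planning contact of section 1.1, say so and name the same operator's earlier CTO PCIs as the reference. Label the comparison exploratory, and state that precision is low and that headset, live proctor and case mix are confounded.
3. Reword 2.2f as describing the listed procedural endpoints in HoloLens-proctored procedures, unless a historical reference is named for it.

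Items 1 and 3 cost a wording amendment and a short form completed by two people after each of ten procedures. Patients and procedures are unaffected. Item 2 adds retrospective data extraction with any approval it needs. Some items, such as costs, may not be in routine records. The downside is more modest claims.

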4.2 Risks, side effects, advantages and disadvantages in participating in the study

Complex CTO PCI is in itself associated with decreased success rate and higher complication risk compared to ordinary PCI in non-occluded vessels. This study group finds no reason to believe there should be safety concerns connected to the use of Hololens guiding as by the described study protocol. The operator who will perform procedures is highly experienced with large volume of CTO procedures and treatment is based on proven treatment techniques. We are confident that interaction between operator and proctor during the CTO PCI may have differentiating potential in terms of procedural outcome due to complexity of CTO and great variation of techniques. In the case of disturbance or operators discomfort with device, the operator will simply remove device and continued procedure in the traditional fashion. We do not see ethical problems in using Hololens in CTO PCI procedures.

5. Patient information and informed consent

Patients will get written information about the study. Informed consent for participation in the study will be obtained from all patients. The patients will be informed that taking part is entirely voluntarily and that they can withdraw for study whenever they want. Withdrawal, or refusal to participate, will not influence treatment. Originals of signed consent forms will stay at the hospital and the patient will get a copy. It is the responsibility of investigators to ensure that informed consent has been acquired.

6. Biological material

Biological material will not be drawn or stored in the study

7. Enrolment period

Enrolment is expected to conclude in first quarter of 2022

8. Publication

Results will be published in a peer reviewed international cardiovascular journal.

9. Study group

A study group is responsible for this protocol, administrates the study implementation and progression.

17.10.2021

1. Fefer, P., et al. Current perspectives on coronary chronic total occlusions: the Canadian Multicenter Chronic Total Occlusions Registry. *J Am Coll Cardiol* 2012; 59: 991-7.
2. Brilakis, Emmanouil S., et al. "Guiding principles for chronic total occlusion percutaneous coronary intervention: a global expert consensus document." *Circulation* 140.5 (2019): 420-433.

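### Does the plan need to name procedural complications and removal of the device as recorded outcomes?

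*Protocol*

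**What the plan says.** The primary objective (Protocol 2.1) concerns communication and teamwork. The secondary objectives (2.2) add usability items, including sterility, comfort and spatial awareness (a), and feasibility of using the device in invasive cardiology (d). Item (e) asks about device limitations: "Does application of HoloLens technology cause limitations, including loss of spatial awareness, spatial disorientation, cabling, battery life and device discomfort". Item (f) asks about procedural results: "Does interaction between operator and proctor affect procedural endpoints like contrast volume, procedure time, fluoroscopy time, costs and procedural success".

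Complications appear only as background. Section 1.1 says that, compared with PCI of a vessel that is not occluded, "CTO PCI has a lower success rate, and a higher complication rate", and section 4.2 repeats the point: "Complex CTO PCI is in itself associated with decreased success rate and higher complication risk compared to ordinary PCI in non-occluded vessels". Section 1.5 adds about the headset: "To our knowledge, this device has never been used in clinical practice connected to interventional cardiology".

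Section 3.3 plans ten procedures in which "the operator uses Hololens during the procedure and communicates with the proctor from the beginning to the end of procedure". Section 4.2 gives the fallback: "In the case of disturbance or operators discomfort with device, the operator will simply remove device and continued procedure in the traditional fashion". Section 3.4 is purely descriptive: means with standard deviations, "median (interquartile range) or no (%) as appropriate".

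**The concern.** Section 1.1 characterises CTO PCI by two outcomes, success and complications, and 2.2(f) names only success. The authors know of no earlier use of the headset in interventional cardiology, and 2.2(e) itself raises disorientation of the person performing the procedure. A reader therefore expects patient harm to be listed. Sterility, contrast volume and fluoroscopy time bear on safety, but they measure process or exposure and not harm to a patient.

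Removal of the device raises a second question. Finishing a case with the headset on is about the most direct sign of feasibility, and section 4.2 anticipates that this may not happen. If removals went unrecorded, the report could not say which cases were guided throughout and which only in part. At stake is whether the published account of a first use can say that patients came to no harm and that the device stayed on.

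**Working it through.** **What is named and what is not.** The sections that could name an outcome or its recording are these:

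| Protocol section | Complications | Removal of the device |
|---|---|---|
| 2.1 Primary objective | not named | not named |
| 2.2(a) usability | not named (sterility is) | not named (comfort is) |
| 2.2(d) feasibility | not named | not named, but falls within it |
| 2.2(e) limitations | not named | not named, but discomfort is, and the list is open (it begins with *including*) |
| 2.2(f) procedural endpoints | not named, but the list is open (it begins with *like*) | not named |
| 3.1, 3.3 to 3.5 | not named | not named |

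The omission is therefore confirmed as *not named*. Nothing in the text supports *will not be collected*.

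**Sections 3.3 and 4.2 side by side.** Section 3.3 states the intention for all ten cases, use throughout. Section 4.2 says what happens if the device disturbs the operator or causes discomfort. An intention and its contingency can both hold. The second trigger is a named item in 2.2(e), and the first fits the spatial-awareness, cabling and battery items there.

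**How partly guided cases are summarised.** Section 3.4 fixes summary formats only. It does not say whether such cases are kept together with the others or shown apart, so a harmful mixing of the two cannot be read out of the protocol. Keeping every started case in one summary is also a legitimate as-planned analysis.

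**What the added outcomes could show.** The protocol gives no sample-size derivation and no complication rate, so there is no figure to reproduce. The only input is n = 10 (section 3.3).

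- Exact (Clopper-Pearson) two-sided 95% interval for 0/10: upper limit 1 − 0.025^(1/10) = 0.308, so 0% to 30.8%. The one-sided 95% upper limit is 1 − 0.05^(1/10) = 0.259.
- 1/10: 0.3% to 44.5%. 2/10: 2.5% to 55.6%.
- Chance of seeing at least one event, 1 − (1 − p)^10, for assumed true rates p (assumptions, since the protocol gives none):

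| Assumed p | Chance of at least one event in 10 |
|---|---|
| 1% | 9.6% |
| 3% | 26.3% |
| 5% | 40.1% |
| 10% | 65.1% |
| 20% | 89.3% |

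A count of zero would be compatible with almost any plausible rate, and a count of one or two would hardly narrow it. Either outcome is useful as a case-by-case listing and not as an estimate. The count-and-percentage format in section 3.4 already accommodates such a listing.

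**The case for a change.** The strongest argument for a change is that the choice of recorded outcomes belongs in the protocol and not in an analysis plan. An open list binds nobody to report complications, and naming success without them commits the authors to only one half of the pair they describe in section 1.1. Recording discomfort is not the same as recording removal, because discomfort can occur without it. The small sample is a reason to list events individually, not to leave them out. Adding two descriptive items would cost little.

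Much of this stands. It is right that outcomes are a protocol matter, that the wording leaves discretion, and that a transparent report would give both items. It does not show that the protocol states something wrong, contradicts itself or fixes a rule badly. The higher risk it cites is that of CTO PCI, which these patients undergo on clinical indication (3.2.1.4), and not a risk attributed to the headset.

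The claim of low cost also needs a limit. The protocol describes no routine complication record, and knowing whether the headset was on when a complication began would need times noted during the procedure. A complication found later may have no clear onset.

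**Conclusion.** No change follows. This is a gap in detail that a competent team fills: complications and device removal are unnamed, but the open lists in 2.2(e) and 2.2(f) and the feasibility objective in 2.2(d) leave room for both. The protocol's own aims, an assessment of a communication tool and of its feasibility in ten uncontrolled cases, would be judged in the same way with or without the extra words. No stated figure is affected. Precision is so low (0% to 30.8% for no events in ten) that no safety conclusion could rest on these counts in any case.

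This rests on two assumptions: that the team notes complications and removals as they occur, and that the report does not present ten cases as evidence of safety. Authors who wish to be explicit could list complications per patient and note removal with its reason, but that is a reporting preference and not a correction.
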